5.1.3 TISSUE DATA AND TRACKING OF BIOLOGICAL SPECIMENS

Tissues and blood samples are entered into the database under the patient's unique study ID number. The information on tissue and blood samples includes date procured, type of tissue, type of preservation, serum, plasma, buffy coat, amount, number of vials, date shipped. Different tissue preservation methods, e.g., formaldehyde-fixed, OCTfixed, flash-frozen, will generate different records. Frozen tissues are intermediately stored at the University of Maryland and shipped in batches, on dry ice, to the NCI. Paraffin-embedded blocks are kept at the University of Maryland Department of Pathology. The tissues and blood samples that are received at the NCI will be entered into an inventory database at the Laboratory of Human Carcinogenesis and will be stored long-term at a contracting facility in Frederick, MD.

5.1.4 DATABASE SETUP

The current system is designed using Access 97. It is housed on a secure Windows Server NT with Windows authentication and only authorized users have access to the shared folder. In addition, the database itself has another layer of security that lets only registered users log on to the application. The database was specifically designed to be a tracking system for all data from hospital cases and the controls recruited through the DMV database.

The database is backed up by the School of Medicine server at the University of Maryland, and also locally by the study data manager. The database has an incremental daily backup, and a regular full back up each weekend. This system is constantly updated.

The database is also used to perform the frequency matching of cases with population-based controls from the DMV database. The DMV data sets are imported into the database and can be searched for matching controls but the contract statistician performs the actual matching. The system has a built-in tool that loads the names and/or addresses into search engines like Yahoo, and if the home phone is found for the candidate control subject, a unique registration number is generated for the person. This study ID number is then used in all subsequent steps. Once a study ID number has been generated, the subjects can be contacted for study eligibility and consent. NCI IRB Approval: Protocol Number: October 28, 2004 05-C-N021

5.2 **RESPONSE CRITERIA**

Not applicable for our study.

5.3 TOXICITY CRITERIA

Not applicable for our study.

5.4 STATISTICAL SECTION

5.4.1 SUMMARY OF STUDY DESIGN AND OBJECTIVES

As of 2010, our last amendment for the study, we are proposing an epidemiological prostate cancer case-control study that will include 1000 prostate cancer cases and a sample of 1000 population-based controls (Table 7). The aim of the study is to identify genetic susceptibility factors for nonhereditary PCa with a particular emphasis on genetic factors that might explain the comparatively aggressive nature of PCa in African-American men. The accrual time is projected to end in 2014/2015, averaging an annual accrual of 120 cases and 120 frequency-matched controls. The participants will be African-American and Caucasian males.

Women are excluded from the study because they do not develop PCa. Men, who are younger than 40 years and older than 90 years are excluded. Nonhereditary PCa is rare at an age younger than 40 years. PCa patients, who are older than 90 years, are excluded because of co-morbidity considerations. Subjects with a race/ethnic background other than African-American or Caucasian have been excluded. Less than 10% of the PCa patients at the 2 participating hospitals have a racial/ethnic background that is not African-American or Caucasian. The inclusion of such a small number of cases would not allow a risk analysis based on stratification by race.

The primary objectives of the study are to examine the association of 1. allele variant genes with PCa risk and outcome, and 2. exposures with gene expression profiles in prostate tumors. The objective will be accomplished with 1) genotype analysis of blood DNA from 1000 cases and 1000 controls, 2) collection of data from questionnaires, medical and pathology records, and the National Death Index, and 3) expression profiling of fresh-frozen tumor samples.

Genome-wide gene expression analysis of prostate carcinomas will compare expression profiles among groups (e.g., African-American versus Caucasian, high versus low IGF-1) that consist of 10-30 tumors per group. The minimum number of tumors needed to generate a molecular profile that differentiates two groups cannot be determined for the proposed experiments. A best estimate is 13 per group based on the following assumptions: A significance level of 0.001 and a power of 0.05, assuming the data is base 2log transformed and that the variance in expression for a gene of interest is 0.5, and that one wishes to be able to detect genes for which one of the four subgroups exhibits a two-fold change in expression at the specified power (using the nQuery software). However, some recent PCa gene expression studies used fewer tissues than we are proposing for our experiments and yielded expression signatures that predicted clinical behavior in response to treatment (84,85) or differentiated tumors according to

NCI IRB Approval:	October 28, 2004
Protocol Number:	05-C-N021

the Gleason score (93). Thus, the proposed sample size for our investigations appears be adequate and is still suitable to do laser-captured microdissection. [name] at the Advanced Computing Center at the NCI-Frederick will conduct the analysis of the expression data.

Target Accrual Numbers of Cases and Controls ¹			
	African-American	Caucasian Males	Total
	Males		
Cases	500	500	1000
Population	500	500	1000
Controls			
Total	1000	1000	2000
¹ Race will be identified by subject self-report			

 Table 7: Target Accrual Numbers for the Proposed Study (as of 2010)

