1.1 STUDY OBJECTIVES

PRIMARY OBJECTIVE

We will examine the association of allele variant genes with PCa risk. The key aim is to examine pathways in relation to PCa, e.g., host defense, inflammation pathways. Within cases, we will examine the relation of genetic variants to molecular, clinical, and prognostic endpoints. The objective will be accomplished with 1) genotype analysis of blood DNA from 1000 cases and 1000 controls and 2) collection of data from questionnaires, medical and pathology records, and the National Death Index. We are testing the hypothesis that susceptibility to nonhereditary PCa is modified by allele variant genes that modulate host defense, inflammation, hormone-stimulated survival and proliferation of mutant cells, the DNA repair capacity, or tumor angiogenesis. The susceptibility may vary by race and lifestyle (gene-environment interaction).

SECONDARY OBJECTIVES

- We will develop gene expression profiles of 60-100 tumors, and will compare gene expression in low-stage and high-stage tumors of African-Americans with gene expression in same stage tumors of Caucasians. The objective is to find gene expression profiles of cancerous and non-cancerous prostate tissue that are characteristic for the disease in African-American men. *We are testing the hypothesis that the molecular signature of primary prostate tumors is different between African-American and Caucasian men. The gene expression profile of African-Americans is associated with an early onset of the disease, a more rapid cancer progression and poor outcome.*
- We will examine the gene expression profiles of tumors from current (n = 10-15) and never smokers (n =10-15). We are testing the hypothesis that current smoking induces a gene signature of tumor progression that reveals the mechanism by which tobacco smoke promotes prostate cancer progression.
- We will determine IGF-1 serum concentrations in our study population and compare gene expression profiles of about 10-15 low-stage tumors from patients with blood IGF-1 levels in the extreme quartiles, respectively. We are testing the hypothesis that a high IGF-1 blood concentration modulates gene expression in primary tumors. The molecular profile is associated with disease progression and poor outcome.

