wild-type genotype (major allele), or the lowest exposure subgroup, as the reference group. Odds ratios and 95% confidence intervals will be calculated by unconditional logistic regression. Regression analysis will be performed in univariate and multivariate models to assess associations between risk factors and cancer susceptibility, and to adjust for possible confounding factors. Case-case analyses, correlating tissue marker expression with tumor staging, hormone blood concentrations, diet or genotypes, will be done by ANOVA, with the student's t-test, or a nonparametric test, such as the Mann-Whitney U rank sum test. To look at trends, the Mantel-Haenszel test for trend will be used to assess the correlation between marker expression/frequency and categorized (e.g., low, medium, high) variables, such as tumor stage, intake of a dietary factor, or IGF-1 blood concentrations. The association between a genotype and outcome will be studied either in a logistic regression model after categorizing into a good and poor outcome group or with the Kaplan-Meier method and the log-rank test. All analyses will be performed with the STATA and SAS statistical software packages.

ANALYSIS OF GENE EXPRESSION PROFILES

The data from the Affymetrix HG-U133A array will be estimated using the RMA procedure from Bioconductor (www.bioconductor.org). Previous analysis on raw data from replicate samples with RMA indicates that the mean standard deviation of log2 intensities is 0.1 across all intensity levels. This corresponds to a typical technical error of 5%-10% (94).

The factorial study design suggests an analysis of variance. We will first examine the four groups for heterogeneity of variances by comparing the ratios of variances between groups to the F-distribution. If the distributions conform, we will follow standard ANOVA procedure. If there is significant departure from agreement, we will perform non-parametric ANOVA using the rank F-test and use the Welch t-test for two group comparisons. We will select differentially expressed genes for contrasts between racial groups at each level of tumor, and for the difference between tumor stages across racial groups. To address the multiple comparisons problem we will use a modified FDR procedure of Benjamini and Hochberg adapted to correlated data (95).

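### The smoking, IGF-1 and vegetable-intake expression contrasts name no race term, although tumors are sampled by race and race is expected to change expression

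*Protocol*

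**What the plan says.** Section 5.4.1 lists among the primary objectives the association of "exposures with gene expression profiles in prostate tumors"; section 1.1 places the expression work under secondary objectives. Section 5.4.1 describes the plan as to "compare expression profiles among groups (e.g., African-American versus Caucasian, high versus low IGF-1) that consist of 10-30 tumors per group", so race and exposure appear as separate comparisons.

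Section 1.1 sets out three exposure contrasts:
- current versus never smokers, 10-15 tumors each, with no stage restriction;
- extreme quartiles of blood IGF-1, about 10-15 low-stage tumors;
- extreme quartiles of tomato and allium intake, about 10-15 low-stage tumors.

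None is matched, stratified or adjusted for race. The same section states: "We are testing the hypothesis that the molecular signature of primary prostate tumors is different between African-American and Caucasian men". Table 6 (section 1.2.4) sets targets by race and stage: 20-30 low-stage and 10-20 high-stage tumors in each race.

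The expression analysis in section 5.4.3 gives one model, the four-group race-by-stage ANOVA, with contrasts for race and stage and no exposure term. Multivariate adjustment for confounders is stated in that section for cancer susceptibility. For tissue markers it says: "Case-case analyses, correlating tissue marker expression with tumor staging, hormone blood concentrations, diet or genotypes, will be done by ANOVA, with the student's t-test", with a rank test and a Mantel-Haenszel trend test as further options. No race term is named there either.

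**The concern.** Race is a sampling stratum, is recorded for every subject by self-report, and is expected by the study itself to alter tumor expression. Stage is held fixed for two of the three exposure contrasts; race is held fixed for none.

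Two different harms can follow, and they are alternatives. If the exposure groups differ in racial make-up, part of the race signature appears as an exposure signature and may be interpreted as a mechanism of smoking, IGF-1 or diet. FDR control does not prevent this, because such genes really do differ between the groups being compared. If the groups happen to be balanced by race, there is little bias, but between-race variation inflates the error and true exposure genes are missed.

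**Working it through.** **Inputs from section 5.4.1.** "A significance level of 0.001 and a power of 0.05"; "the variance in expression for a gene of interest is 0.5" (log2 scale); a two-fold change, 1 log2 unit, where "one of the four subgroups exhibits a two-fold change in expression at the specified power"; 13 tumors per group.

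**The plan's own figure.** With two-sided alpha 0.001, n per group = 2 × variance × (z_alpha/2 + z_power)² / delta².
- Power read as 0.95: 2 × 0.5 × (3.29 + 1.645)² = 24.4, so 25.
- Power taken literally as 0.05: 2 × 0.5 × (3.29 − 1.645)² = 2.7, so 3.
- With 0.5 read as the SD (variance 0.25) and power 0.95: 12.2, so 13.

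The 13 does not reproduce as printed. That is a separate matter and this point does not rest on it. I keep variance 0.5 and 13 per group as stated.

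**Assumptions not in the protocol.** Race effect R of 0.5 or 1 log2 unit (a two-fold difference is 1), variance 0.5 within race, and the racial make-up of each exposure group.

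**Race balanced: loss of power.** Leaving out a 50/50 race factor adds R²/4 to the variance. For R = 1 it becomes 0.5 + 0.25 = 0.75, equivalent to 1.5 times the sample size. Noncentral t, difference 1, noncentrality = 1/√(2 × variance/13):
- race omitted, variance 0.75: noncentrality 2.94, 24 df, power 0.251;
- race in the model, variance 0.5: noncentrality 3.61, 23 df, power 0.459;
- cost if race has no effect: 0.466 (24 df) falls to 0.459 (23 df).

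For R = 0.5 the gain is small: simulated power with a 7 v 6 split is 0.43 without race and 0.45 with it. If 0.5 was meant as the SD, the R = 1 figures at 7 v 6 are 0.55 and 0.88.

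**Race unbalanced: bias.** Spurious difference = R × (difference in race share). False-positive rates at alpha 0.001, 13 per group, variance 0.5, no exposure effect, by simulation with the race of each tumor drawn at the stated share:

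| Race effect R | Shares | Spurious difference (log2) | Race omitted |
|---|---|---|---|
| 1 | 65/35 | 0.30 | 0.8% |
| 1 | 60/40 | 0.20 | 0.34% |
| 0.5 | 65/35 | 0.15 | 0.24% |
| 0.5 | 60/40 | 0.10 | 0.16% |

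With race in the model the rate returns to about 0.1%. With the split held fixed, simulation gives:
- 8 v 5, R = 0.5: 0.11%;
- 8 v 5, R = 1: 0.07%, below nominal, because the inflated variance outweighs the bias;
- 9 v 4, R = 1: 0.36%;
- 10 v 3, R = 1: 1.9%.

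For scale, a 0.5 SD race difference in an exposure would make pooled extreme quartiles about 66/34, and 0.3 SD about 59/41. Both shifts are assumptions.

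**Chance imbalance.** If half the men are of each race and race is unrelated to exposure, the binomial probability that the two groups' shares differ by 0.3 or more is 26% at 10 per group, 17% at 13 and 10% at 15. Averaged over all draws the test then keeps about its nominal level. The harm is conditional on the split obtained, and every race gene measured on those tumors shares it.

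**The case against.** The strongest reply is that the protocol is silent rather than wrong. Section 1.1 says which tumors are compared, not with which model, and covariates may be left to an analysis plan not at hand. This has force: nothing says that the contrasts will be unadjusted. But section 5.4.3 does set out the factors, tests, contrasts and FDR procedure for expression data, and exposure together with race is not among them.

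Three stronger readings are tempting and are not supported.
- A reader might take the instruction to "use the Welch t-test for two group comparisons" as proof of an unadjusted exposure test. In context it is the fallback when variances differ in the four-group ANOVA, and the contrasts listed next concern race and stage.
- A reader might say that the tissue-marker tests are all two-group comparisons that ignore race. ANOVA and a trend test are also listed, ANOVA can carry race, and section 5.4.3 says that cases are pooled and then examined by race. That sentence follows one on occurrence, stage and outcome, so its reach to tissue markers is arguable. The most that can be said is that no race term is named.
- A reader might infer that false signatures are certain. Table 6 sets equal race targets within each stage, so sampling by itself creates no imbalance between exposure groups, and the protocol gives no race distribution for smoking, IGF-1 or vegetable intake.

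It is also fair that a two-fold race effect is as large as the target effect, and that milder inputs give much smaller distortion. Adjustment can also lower power: with a 10 v 3 split the adjusted power is 0.28. The unadjusted 0.85 in that setting (R = 1) is inflated by the bias.

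**Conclusion.** The point holds in a limited form. Run as described, the three exposure contrasts leave out a factor that the study samples on and expects to matter. The result is either loss of power or a risk that race genes are labelled as exposure genes, depending on how race falls across the groups.

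The power figures, 0.25 against 0.46, apply to a gene with two-fold effects of both race and exposure, race balanced, and 0.5 as the within-race variance. The bias has no known size; the tabulated rates depend on assumed race effects and shares. Alpha 0.001 comes from the sample-size paragraph, whereas genes will be selected by an FDR procedure, so these rates are a guide to direction and order of magnitude. This is a worthwhile low-cost improvement to an exploratory analysis and does not invalidate the plan.

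**What to change.** In section 5.4.3, state that each exposure contrast is tested per gene in a linear model with additive main effects for exposure and race, plus stage for smoking, where stage is not already fixed. Additive terms are enough: for smoking that is four parameters including the intercept, which leaves 16-26 residual degrees of freedom from 20-30 tumors. A full crossing of race, stage and exposure would spread the same tumors over eight cells.

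For the case-case tissue-marker tests, add race to the ANOVA, or use a race-stratified rank or trend test.

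The exposure quartiles can stay as they are. Redefining them within race would change the question, since men with the same IGF-1 level could fall in different groups.

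No new data are needed. The race term costs one degree of freedom (power 0.466 to 0.459 at 13 per group if race has no effect), and power is lower where race and exposure are correlated. Reporting the racial make-up of each exposure group would show readers which situation applies.

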Recent progress in whole genome expression profiling has generated prognosisrelated molecular profiles for many cancer types (81-83). A four-gene expression model has been described that discriminated between seven PCa patients with relapse and seven PCa patients without relapse, independently of stage and grade (84). The gene expression profiles were obtained from clinically localized tumors that were removed by radical prostatectomy. Another research group studied a group of 23 PCa patients, who were treated with adjuvant androgen suppression therapy before surgery (85). The surgical specimens were investigated for correlations between a patient's gene expression profile and disease recurrence with a 5-year follow-up. An eight-gene signature was identified that classified patients into a PCa recurrence group and a non-recurrence group with an overall correct prediction of 83%. A combination of gene profile and clinical/pathological parameters yielded a correct prediction of 96%.

Although these investigations have shown that gene expression profiles can predict PCa recurrence, there is no such study in the literature that has attempted to identify the genes and pathways with relevance to the etiology and aggressive behavior of PCa in African-Americans. Our objective is to find molecular signatures of low-stage and high-stage tumors in African-Americans, and to identify genes that are relevant to metastasis and patient outcome. The research is also aimed at determining molecular profiles in the context of lifestyle and diet if a strong association between a lifestyle/dietary component and cancer risk has been reported or can be established in our study population. We expect to collect up to 100 fresh-frozen tumor specimens that 1) are primarily identified by PSA screening, 2) are positive for cancer by needle biopsy, and 3) are surgically removed by radical prostatectomy. Of those, we expect that about 25% of the patients will have an advanced pathological stage (\geq pT3) or a Gleason score \geq 7 (86). Of the 52 patients, who underwent radical prostatectomy at the 2 participating hospitals in 2001, 49 were informative for staging and 24.5% of these had an advanced pathological stage (Table 5).

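### The 13 tumors per group for expression profiling does not follow from its printed inputs; the power is misprinted and it is unclear whether 0.5 is a variance or an SD

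*Protocol*

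**What the plan says.** Protocol section 5.4.1 first says that the minimum number of tumors cannot be determined. It then gives a figure: "A best estimate is 13 per group based on the following assumptions: A significance level of 0.001 and a power of 0.05". The other inputs are log2-transformed data, "the variance in expression for a gene of interest is 0.5", and the aim of detecting genes for which "one of the four subgroups exhibits a two-fold change in expression at the specified power (using the nQuery software". The section then notes that some published expression studies used fewer tissues, and concludes that the proposed size seems adequate. Planned groups run from 10 to 30 tumors.

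Section 1.1 sets the smaller comparisons. For smoking: "We will examine the gene expression profiles of tumors from current (n = 10-15) and never smokers (n =10-15". The IGF-1 and vegetable-intake comparisons use about 10-15 low-stage tumors from patients in the extreme quartiles. Section 1.2.4, Table 6, plans 20-30 low-stage and 10-20 high-stage tumors per race. Section 5.4.3 plans an analysis of variance over four groups, with two-group comparisons.

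**The concern.** Nobody designs for 5% power, so "a power of 0.05" cannot be the target. The natural reading is a type II error of 0.05, that is, power 0.95. With that correction the remaining inputs should return 13, and with a variance of 0.5 they do not.

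The 13 is the only numerical sample-size argument for the expression work, which section 1.1 lists as secondary and section 5.4.1 places among the primary objectives. It also describes a four-subgroup comparison, whereas the smoking, IGF-1 and diet hypotheses compare two groups of 10-15. If the true sensitivity is well below what the sentence implies, a null result in those comparisons would be read as more informative than it is.

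**Working it through.** **Inputs** (section 5.4.1): alpha 0.001 per gene; shift d = log2(2) = 1; subgroup means (1, 0, 0, 0); variability 0.5. The tests below are two-sided. Sidedness is not stated, and one-sided testing lowers the 28 below to 25. The 10-15 for IGF-1 and diet is taken to mean per quartile.

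**Four-group F test.** The grand mean is 0.25, so the sum of squared deviations is 0.75² + 3 × 0.25² = 0.75. The noncentrality is λ = 0.75n/σ², with 3 and 4(n − 1) degrees of freedom.
- Variance 0.5: λ = 1.5n (19.5 at n = 13).
- SD 0.5, i.e. variance 0.25: λ = 3n (39 at n = 13).

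**Two-group t test.** The noncentrality is δ = d/(σ√(2/n)), with 2n − 2 degrees of freedom.
- Variance 0.5: δ = √n (3.61 at n = 13).
- SD 0.5: δ = √(2n) (5.10 at n = 13).

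**Step 1: can 13 be reproduced?** Smallest n per group:

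| Reading | Four-group F | Two-group t |
|---|---|---|
| As printed: power 0.05, variance 0.5 | 5 | 6 |
| Power 0.95, variance 0.5 | 22 | 28 |
| Power 0.95, SD 0.5 | **13** | 15 |

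In the third row, F-test power is 0.949 at 12 and 0.971 at 13, so the match to 13 is exact. With variance 0.5, even 80% power needs 17 (F) or 20 (t).

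**Step 2: power at the planned sizes for a two-fold change**

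| n per group | F, variance 0.5 | t, variance 0.5 | F, SD 0.5 | t, SD 0.5 |
|---|---|---|---|---|
| 10 | 0.38 | 0.28 | 0.86 | 0.70 |
| 13 | 0.61 | 0.47 | 0.97 | 0.89 |
| 15 | 0.73 | 0.58 | 0.99 | 0.95 |
| 20 | 0.92 | 0.81 | >0.99 | >0.99 |
| 30 | >0.99 | 0.97 | >0.99 | >0.99 |

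**Step 3: change detectable with 95% power, two-group t test.** Solve the t-test power for d and report 2^d.
- Variance 0.5: d = 1.85 at n = 10 (3.6-fold), 1.55 at 13 (2.9-fold) and 1.41 at 15 (2.7-fold).
- SD 0.5: d = 1.31 at n = 10 (2.5-fold), 1.09 at 13 (2.1-fold) and 1.00 at 15 (2.0-fold).

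**Step 4: other routes to about 13 with variance 0.5.** A contrast of one subgroup against the other three needs 18 at power 0.95 and 13 at power 0.80. A main effect with the two-fold change in two of the four subgroups needs 14 at power 0.95. The first reaches 13 only with a different power, and the second changes the effect pattern that the text states.

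**The case against.** The best defence is that 13 is right and only its labels are wrong. The four-group F test, which is the design that section 5.4.1 describes and section 5.4.3 plans to analyse, returns exactly 13 at alpha 0.001, power 0.95 and SD 0.5. That points to two slips: power written for type II error, and variance written for SD. This is plausible and may well be what happened. The document does not establish it, however, and the two readings differ by 9 tumors per group for the four-group test (22 against 13) and 13 for the two-group test (28 against 15).

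The protocol also hedges. It calls 13 a best estimate, says that the minimum cannot be determined, and rests its adequacy conclusion partly on smaller published studies; section 1.2.4 describes one of seven against seven patients and one of 23 in total. That is a separate argument and it stands on its own terms. It does not reconcile a calculated figure with inputs that fail to produce it.

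Three stronger readings should be resisted.
- A reader might infer that the printed inputs require 22-28 per group. They do so only after power is changed to 0.95 while the variance is left alone.
- A reader might infer that the adequacy claim fails for all groups of 10-15, or for the race comparison. With SD 0.5, two-group power at 15 is 0.95. The 20-30 low-stage tumors per race give two-group power of 0.81-0.97 even with variance 0.5.
- A reader might infer that Table 6 is unattainable. A 24.5% high-stage rate in 100 specimens gives about 24.5 tumors, or about 12 per race, which lies inside the planned 10-20.

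**Conclusion.** The sample-size statement is wrong as written. The printed power cannot be intended, and no reading that keeps the printed variance, the stated four-group F test and a 0.95 target gives 13. Whether the n is also wrong cannot be settled from the document. At power 0.95 the requirement is 13 (four-group) and 15 (two-group) if 0.5 is the SD, or 22 and 28 if it is the variance.

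One consequence holds on both readings. Two-group comparisons at 10 per group have power 0.28 or 0.70 for a two-fold change, short of 0.95, and 10-12 per group is below the protocol's own 13. How serious the shortfall is for the rest of the 10-15 range depends on the answer.

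This rests on reading the power as 0.95, two-sided tests, equal groups and 10-15 per quartile for IGF-1 and diet. The case-control sample size and genotype power tables are not affected.

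**What to change.** In section 5.4.1:
1. Correct the power, presumably to 0.95.
2. State whether 0.5 is the variance or the SD of log2 expression.
3. Restate the n per group to match: 22 for the four-group test and 28 for two-group comparisons if it is the variance, or 13 and 15 if it is the SD.
4. Qualify the adequacy statement for groups below those sizes by giving the power or the detectable fold change at 10-15 per group, for which the figures above can be used.

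The cost is protocol wording. No added enrolment follows from this point. The downside is that the stated sensitivity becomes less favourable: slightly if 0.5 is the SD, and markedly if it is the variance.
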